7.4 Vital Signs and Weight

7.4.1 Vital Signs in Part A

On the Day -1 for each dosing period the blood pressure, pulse rate, and temperature for each subject in Part A will be collected. At each collection time point all vital signs are to be collected after the subject has been supine for at least 5 minutes. Then, to assess orthostatic hypertension, measurements of blood pressure and pulse rate will be collected in triplicate at 1, 2, and 3 minutes after rising to a standing position. Vital signs will be similarly assessed at 2, 4, and 8, 24, 48, and 96 hours after dosing for each subject. At each time point, the maximum value among the triplicate standing measurements will be obtained, and the change from the supine measurement will be derived for the triplicate maximum.

Descriptive statistics for the supine measurement and triplicate maximum along with the change from supine for the triplicate maximum will be tabulated for each treatment group, except the 30mg fed treatment group, at each time point.

Subjects will be determined to have orthostatic hypotension if either of the following occur after the subject rises from a supine to standing position.

- Systolic blood pressure decreases ≥ 20 mmHg, or
- Diastolic blood pressure decreases ≥ 10 mmHg.

In addition, subjects with the following increases in the pulse rate after rising from a supine to standing position will be tabulated.

- Pulse rate increases ≥ 20 beats per minute (bpm),

The number (percent) of subjects having orthostatic hypotension and pulse rate increases will be tabulated by treatment group. The percentage will be calculated using the number of subjects in the Safety population with data at the time point as the denominator.

Change from baseline statistics will also be defined for the supine measurements of blood pressure, pulse rate and temperature using the pre-dose values as baseline. Descriptive statistics for the supine measurement of temperature will also be provided by treatment group.

Plots of the mean \pm standard error for each vital sign, collected while supine, over time (baseline through Day 4 [96 hours]) will be provided by treatment group.

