7.4.2.1 Vital Signs over time in Part B

For the pre-dose and follow-up assessments on Days 1, 2, 7, 14, 21, and 29 and Days 35 and 42, respectively, the maximum value among the triplicate standing measurement will be obtained, and the change from the supine measurement will be derived for the triplicate maximum.

Descriptive statistics for the supine measurement and triplicate maximum along with the change from supine for the triplicate maximum will be tabulated for each treatment group at each time point.

Subjects will be determined to have orthostatic hypotension using the criteria provided in Section 7.4.1. The number (percent) of subjects having orthostatic hypotension will be tabulated by treatment group. The percentage will be calculated using the number of subjects in the Safety population with data at the time point as the denominator.

Change from baseline statistics will also be defined for the supine measurements of blood pressure, pulse rate and temperature using the Day 1 values as baseline. Descriptive statistics for the supine measurement of temperature will also be provided by treatment group.

Plots of the mean \pm standard error for each vital sign, collected while supine, over time (baseline through Day 4 [96 hours]) will be provided by treatment group.

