7.4.2.3 Clinically Significant Vital Sign Change in Part B

The number (percent) of subjects who experience either orthostatic hypotension or a clinically significant deviation in vital signs while on-treatment will be tabulated by treatment group. Vital sign normal are defined as follows:

- Pulse rate < 50 bpm or > 100 bpm,
- Systolic blood pressure either ≤ 90 mmHg or ≥ 160 mmHg,
- Diastolic blood pressure either ≤ 50 mmHg or ≥ 100 mmHg.

All on-treatment values, including unscheduled assessments, will be considered, and the denominator for the percentages will be the number of subjects in the Safety Population.

All subjects who have a clinically significant change in vital signs or orthostatic hypotension will be documented in a by-subject listing. The listing will include all of the vital sign measurements

from the study for the subject, and abnormal values will be flagged. A similar listing for the data from Part A will also be produced, but no a summary table of the results as are planned for Part A.

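### The SAP tabulates postural blood pressure change only from the highest of three standing readings, so the table largely masks a fall present at only one or two of the three minutes

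*SAP*

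**What the plan says.** Protocol 10.4.2 and SAP 7.4.1 take standing blood pressure and pulse at 1, 2 and 3 minutes after a supine reading. SAP 7.4.1 then reduces the standing readings to one: "the maximum value among the triplicate standing measurements will be obtained, and the change from the supine measurement will be derived for the triplicate maximum". That is also what is reported: "Descriptive statistics for the supine measurement and triplicate maximum along with the change from supine for the triplicate maximum will be tabulated". SAP 7.4.2.1 (Part B, pre-dose and follow-up) and 7.4.2.2 (Part B, 4 hours post-dose) use the same rule, for example "the maximum value among the triplicate standing measurement will be obtained". It applies to pressure and pulse alike.

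The other continuous summaries do not use the standing readings. "Change from baseline statistics will also be defined for the supine measurements of blood pressure, pulse rate and temperature", and the plots show the mean and "standard error for each vital sign, collected while supine, over time".

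The postural criteria in SAP 7.4.1 are a systolic fall of at least 20 mmHg or a diastolic fall of at least 10 mmHg (orthostatic hypotension), and a pulse rise of at least 20 bpm. The flag is worded "Subjects will be determined to have orthostatic hypotension if either of the following occur after the subject rises from a supine to standing position", without saying which standing reading decides it. The purpose, however, is given as "to assess orthostatic hypertension, measurements of blood pressure and pulse rate will be collected in triplicate", and no criterion for a postural rise in pressure follows. The pressure limits in SAP 7.4.2.3 are absolute values, not postural changes.

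**The concern.** One rule serves two variables whose criteria point in opposite directions. The highest standing pulse is the worst case for a rise. The highest standing pressure is the best case for a fall. The only planned summary of how far pressure changes on standing is therefore built from the reading least able to show the event that the SAP defines.

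Changes in vital signs are part of the primary safety endpoint (Protocol 11.3.1.2) of a first-in-man ascending-dose study. At stake is whether the change table can show the size, and any dose trend, of a brief postural fall, including falls too small to reach the flag threshold.

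**Working it through.** The plan gives no figure to reproduce on this point. The first step is an identity; the rest measures its effect.

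**1. Identity.** Supine minus the highest standing reading equals the smallest of the three supine-minus-standing differences. Example: supine systolic 130, standing 108, 115 and 124. The falls are 22, 15 and 6. The tabulated change is −6, although the 1-minute fall of 22 meets the criterion of 20.

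**2. Inputs.** From the documents: three standing readings per assessment, a systolic criterion of 20 mmHg, and in Part B 8 active subjects per dose with 4 × 2 = 8 pooled placebo subjects. Assumed, because the documents give no SD: 4, 6 or 8 mmHg per reading, independent normal errors on the supine reading and on each standing reading, and no between-subject spread in the true response. Each scenario used 1,000,000 simulated assessments.

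**3. No true fall.** The expected maximum of three normal readings is 3/(2√π) = 0.846 SD above their mean, and the minimum is 0.846 SD below. The highest-reading change is shifted by +3.4/+5.1/+6.8 mmHg, the lowest-reading change by −3.4/−5.1/−6.8, and a single-minute change by 0.

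**4. Tabulated drug-minus-placebo change (mmHg, SD 4/6/8).**

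| True fall at minutes 1, 2, 3 | Highest reading (SAP) | Lowest reading | Minute 1 |
|---|---|---|---|
| 20, 20, 20 | −20.0 | −20.0 | −20.0 |
| 20, 20, 0 | −3.4/−5.0/−6.4 | −18.9/−18.3/−17.8 | −20.0 |
| 20, 10, 0 | −3.3/−4.6/−5.5 | −16.7/−15.4/−14.5 | −20.0 |
| 20, 0, 0 | −1.1/−1.7/−2.2 | −16.6/−15.0/−13.6 | −20.0 |

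The last row can be checked by hand. When the minute-1 fall is large relative to the SD, the highest reading is in effect the larger of the other two, whose expectation is 1/√π = 0.564 SD. The difference from placebo is then 0.846 − 0.564 = 0.282 SD, or 1.1/1.7/2.3 mmHg. This ceiling does not grow with the size of the fall.

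**5. Against sampling error, 8 versus 8, fall at minute 1 only.**

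| Summary | SE of difference, SD 4/6/8 | Difference in SEs |
|---|---|---|
| Highest | 2.55/3.82/5.08 | 0.4/0.4/0.4 |
| Lowest | 2.67/3.99/5.26 | 6.2/3.8/2.6 |
| Minute 1 | 2.83/4.24/5.66 | 7.1/4.7/3.5 |

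Any between-subject spread would raise the SEs and lower all three ratios.

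**6. What the flag would show (systolic criterion, fall of 20 mmHg at minute 1 only).** Applied to any standing reading, it counts about 50% of active assessments (the minute-1 change is centred on −20, so half lie at or beyond it), against 0.1%/2.4%/9% with no true fall. Computed from the derived maximum, it would count under 1%.

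**The case against.** The strongest reply is that postural falls have their own output. Hypotension counts by treatment group are planned in SAP 7.4.1, 7.4.2.1 and 7.4.2.2. SAP 7.4.2.3 adds a Part B table for which "All on-treatment values, including unscheduled assessments, will be considered", and a listing of every vital sign of flagged subjects, with a similar listing for Part A. On the natural reading of the flag, the brief fall in step 6 would be seen in about 4 of 8 active subjects at a time point, against fewer than 1 of 8 on placebo. This stands. A reader might infer that the SAP would miss orthostatic hypotension or understate its count. The documents do not support that, because nothing ties the flag to the maximum. What remains is that a count does not show size, and that brief falls below the threshold appear in neither the counts nor, to any useful extent, the change table.

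The minute-1-only profile is also an extreme case, and nothing in the documents predicts it. That is fair: for a sustained fall nothing is lost. Readings a minute apart may be correlated. At correlation 0.5 the no-effect shift is multiplied by √0.5, giving 2.4/3.6/4.8 mmHg, but correlation does not remove the masking.

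The maximum would suit the purpose as written, orthostatic hypertension. Whether that word is a slip cannot be told from the documents, but no matching criterion exists.

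Two further inferences fail. Escalation is not shown to be affected: this is a descriptive summary, and Protocol 8.3.1 rests the decision on a wider review of safety data. Nor does the Part A group list in SAP 2.2.2 show that a placebo column is missing: the same section names placebo among the Part A treatments, SAP 7 plans placebo summaries, and the table formats are in companion documents not available here.

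**Conclusion.** The point holds, within limits. That the tabulated pressure change is the smallest observed fall is an identity and needs no assumption. It conflicts with the direction of the SAP's only postural pressure criterion, and no other continuous summary uses the standing readings. The harm is confined to falls present at one or two of the three minutes. In the extreme case an assumed 20 mmHg fall is tabulated as about 1 to 2 mmHg, given the assumed SDs of 4 to 8 mmHg and independent readings. The counts and listings limit the harm, provided that the flag is applied to each standing reading, which the SAP should say. Severity is minor to moderate: a descriptive table within the primary safety endpoint.

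**What to change.** In SAP 7.4.1, 7.4.2.1 and 7.4.2.2:

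- For systolic and diastolic pressure, tabulate the change from supine at each of minutes 1, 2 and 3. Optionally add the change for the lowest standing reading, labelled as worst case and read against placebo. Keep the maximum for pulse rate.
- State that the existing hypotension criteria are applied to each standing reading and not to the derived maximum.
- Reconcile the stated purpose in 7.4.1 (hypertension) with the hypotension criterion that follows. If a postural rise in pressure is also of interest, keep the maximum for pressure as a second, labelled summary.

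The cost is SAP wording and three rows in place of one, plus one derived variable if the lowest reading is added. No new data are needed. Per-minute changes carry no extreme-value shift but are slightly noisier (SE 2.8/4.2/5.7 mmHg, against 2.6/3.8/5.1 for the maximum). The lowest reading carries a downward shift of about 0.85 SD in every arm, which is why it should not stand alone.

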7.4.2 Vital Signs in Part B

Orthostatic blood pressure and pulse rate along with temperature will be collected pre-dose on Days 1, 2, 7, 14, 21, and 29, at 4 hours post-dose on Days 1 and 28, and as follow-up assessments on Days 35 and 42. Data summaries will be created using the pre-dose and follow-up assessments, and a separate summary will examine the 4-hour post-dose measurements. The orthostatic blood pressure and pulse rate measurements collected on Days -6, -2, -1 and 27 along with all unscheduled vital sign assessments will be provided in the listings but will not be included in the summary tables or figures.

7.4.2.1 Vital Signs over time in Part B

For the pre-dose and follow-up assessments on Days 1, 2, 7, 14, 21, and 29 and Days 35 and 42, respectively, the maximum value among the triplicate standing measurement will be obtained, and the change from the supine measurement will be derived for the triplicate maximum.

Descriptive statistics for the supine measurement and triplicate maximum along with the change from supine for the triplicate maximum will be tabulated for each treatment group at each time point.

Subjects will be determined to have orthostatic hypotension using the criteria provided in Section 7.4.1. The number (percent) of subjects having orthostatic hypotension will be tabulated by treatment group. The percentage will be calculated using the number of subjects in the Safety population with data at the time point as the denominator.

Change from baseline statistics will also be defined for the supine measurements of blood pressure, pulse rate and temperature using the Day 1 values as baseline. Descriptive statistics for the supine measurement of temperature will also be provided by treatment group.

Plots of the mean \pm standard error for each vital sign, collected while supine, over time (baseline through Day 4 [96 hours]) will be provided by treatment group.

7.4.2.2 Post-dose (4-hour) Vital Signs in Part B

For the 4-hour post-dose assessments on Days 1 and 28 the maximum value among the triplicate standing measurement will be obtained, and the change from the supine measurement will be derived for the triplicate maximum.

Descriptive statistics for the supine measurement and triplicate maximum along with the change from supine for the triplicate maximum will be tabulated for each treatment group at each time point. Subjects will be determined to have orthostatic hypotension using the criteria provided in Section 7.4.1. The number (percent) of subjects having orthostatic hypotension will be tabulated by treatment group. The percentage will be calculated using the number of subjects in the Safety population with data at the time point as the denominator. Descriptive statistics for the supine measurement of temperature will also be provided by treatment group.

7.4.2.3 Clinically Significant Vital Sign Change in Part B

The number (percent) of subjects who experience either orthostatic hypotension or a clinically significant deviation in vital signs while on-treatment will be tabulated by treatment group. Vital sign normal are defined as follows:

- Pulse rate < 50 bpm or > 100 bpm,
- Systolic blood pressure either ≤ 90 mmHg or ≥ 160 mmHg,
- Diastolic blood pressure either ≤ 50 mmHg or ≥ 100 mmHg.

All on-treatment values, including unscheduled assessments, will be considered, and the denominator for the percentages will be the number of subjects in the Safety Population.

All subjects who have a clinically significant change in vital signs or orthostatic hypotension will be documented in a by-subject listing. The listing will include all of the vital sign measurements

from the study for the subject, and abnormal values will be flagged. A similar listing for the data from Part A will also be produced, but no a summary table of the results as are planned for Part A.

7.4.3 Anthropometric variables in Part B

Weight plus waist, hip and neck circumference will be collected on Days -1, 7, 14, 21, and 29, and at the follow-up assessments times on Days 35 and 42 or 56.

Change from baseline statistics will be defined for each parameter using the Day -1 values as baseline; descriptive statistics for each parameter will also be tabulated by treatment group.

Plots of the mean \pm standard error for weight over time (baseline through Day 56) will be provided by treatment group.

7.5 Electrocardiograms

Subjects must be supine for at least 5 minutes prior to and remain awake during each 12-lead, digital, triplicate electrocardiogram (ECG) collection. ECGs will be read by a qualified physician at the site to document parameter measurements and to determine any clinically relevant findings. The triplicate numeric measurements will be averaged at each time point to obtain the value that will be used for analyses, while the most severe interpretation (Normal; Abnormal, not Clinically Significant; Abnormal, Clinically Significant) among the triplicate measurements will be used for analyses. However, all abnormalities documented on any of the triplicate measurements will be reported in the listings. The investigator, or qualified designee, will report any new clinically relevant finding from any of the triplicate measurements as an AE.

7.5.1 ECGs in Part A

In Part A, triplicate ECGs will be collected during each dosing period at pre-dose and at 2, 4, 6, 8, 12, 24, 48, and 96 hours post-dose. The parameters heart rate, PR interval, QRS duration, QT interval, RR interval, QTc Bazett, and QTc Fridericia (QT_{Cf}) will be obtained as the mean of the triplicate measurements for each ECG collection, plus the investigator will provide an overall ECG evaluation.

7.5.1.1 Descriptive Summary of ECGs

At each time point, the change from baseline will be derived for each numeric parameter using the pre-dose value as baseline. Descriptive statistics for the value of each parameter at each time point and the change from baseline for each parameter at each post-dose time point will be provided by treatment group.

Plots of the mean \pm standard error for the changes from baseline in each parameter over time will be provided by treatment group.

The single tracing collected at Screening and the triplicate measurements collected on the Day -1 for each dosing interval will be included in by-subject listings but will not be included in any summary tables.

7.5.1.2 Exposure Response Analysis for QT_{cf}

To evaluate the effect of LY3202328 on QTc prolongation, QT_{cf} will be assessed across a range of concentrations using concentration response modeling. The changes in QT_{cf} at the time points 2, 4, 6, 8, 12, and 24 post-dose, where PK blood samples are also collected, will be modeled with drug concentration as a continuous covariate, treatment (LY3202328 or placebo) and time as fixed effects, and a random effect for subject within dosing period. This random effect introduces correlation among a subject's QT_{cf} measurements with a dosing period, but the measurements from different dosing intervals will be treated as independent. Estimates of the regression coefficient and the treatment effect along with their associated 90% confidence intervals (CIs) will be obtained from the model.

The predicted mean placebo-adjusted change from baseline in QT_{cf} will be obtained by multiplying the estimated regression coefficient and the observed geometric mean Cmax and adding the estimate of the treatment effect (LY3202328 – Placebo). An estimate of the 90% CI for the predicted mean placebo-adjusted change from baseline in QT_{cf} will be bootstrapped using 5000 resamples with subject within dosing interval as the resampling unit. For each resample the model will be fitted and the predicted estimate obtained using the geometric mean Cmax based on the resample. The CI will be determined from the distribution of the resampled predicted values.

If the upper bound of the 90% CI does not exceed 10 ms then a clinically relevant QT effect can be excluded.

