7.5.2.2 Clinically Significant ECGs in Part B

The number (percent) of subjects who either had an abnormal ECG (regardless whether clinically significant or not) or had a clinically significant change in the QT_{cf} value while on-treatment will be tabulated by treatment group. Abnormal QT_{cf} values will be determined using the following criteria:

- $QT_{cf} \geq 480$ msec
- $QT_{cf} \geq 500$ msec
- $QT_{cf} \geq 550$ msec
- Change from baseline in $QT_{cf} \geq 30$ msec
- Change from baseline in $QT_{cf} \geq 60$ msec.

All on-treatment values, including unscheduled assessments, will be considered, and the denominator for the percentages will be the number of subjects in the Safety Population.

All subjects who have an extreme QT_{cf} value or orthostatic value will be documented in a by-subject listing. The listing will include all of the ECG measurements from the study for the subject, and the noteworthy values will be flagged. A similar listing for the Part A will also be produced, but no summary table of the results is planned for Part A.

8 Pharmacokinetic Analyses

The PK analysis for the study will be detailed in a separate PK SAP.

9 Exploratory PK/PD and PK/Biomarker Analyses

The exploratory PK/PD and PK/biomarker analyses for the study will be detailed in a separate SAP.

10 Additional, non-PK, Analyses for the DDI study

Any additional non-PK analyses for the DDI study will be detailed in a separate SAP.

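### The Part A QTcF rule excludes a QT effect with no dose or concentration limit, from one prediction at a geometric mean Cmax whose dose level is not named

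*SAP*

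**What the plan says.** SAP 7.5.1.2 states that QTcF "will be assessed across a range of concentrations using concentration response modeling". The model for change in QTcF has concentration as a continuous covariate, a two-level treatment factor (LY3202328 or placebo), time, and a random effect for subject within dosing period. The predicted placebo-adjusted change is then obtained by "multiplying the estimated regression coefficient and the observed geometric mean Cmax and adding the estimate of the treatment effect". Its interval is "bootstrapped using 5000 resamples with subject within dosing interval as the resampling unit", and in each resample the model is refitted and "the predicted estimate obtained using the geometric mean Cmax based on the resample". The decision rule is: "If the upper bound of the 90% CI does not exceed 10 ms then a clinically relevant QT effect can be excluded".

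No dose level, food state or concentration is attached to the Cmax or to the conclusion. SAP 2.2.2 lists Part A doses of 1, 3, 10, 30, 100 and 300 mg, with 600 mg possible, plus 30 mg fed. SAP section 8 adds: "The PK analysis for the study will be detailed in a separate PK SAP".

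**The concern.** A linear concentration model gives a different predicted effect at every concentration, so a 10 ms rule means something only once the exposure is named. Here the doses span 300-fold and the rule uses one unlabelled value.

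The singular Cmax, the single interval and the one Cmax per resample, with no dose strata mentioned, all point to a geometric mean over all active subject-periods. Such a mean sits near the middle of the dose range on the log scale, far below the top dose. The report could then say that a QT effect is excluded when the same fitted model predicts one at the highest dose. This is the only formal QT conclusion for Part A: SAP 7.5.2.2 plans a listing of extreme QTcF values for that part, but no summary table.

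**Working it through.** **Inputs.** Six LY subjects per dose level if all are retained (Protocol 8.2), so dose levels weigh equally in a pooled mean. Predicted 24-hour AUC in Table GSEA.1 (Protocol 6.5): 0.6 at 1 mg, 7.8 at 13 mg and 114 at 300 mg, with a maximum absorbable dose of 190 mg (footnote b). Protocol 4.2 says Cmax rose less than proportionally with dose in preclinical work and gives no exponent. No human Cmax is given, so AUC stands in for it.

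**Reproducing the protocol's figures.** AUC = 0.6 × min(dose, 190) gives 0.6 × 1 = 0.6, 0.6 × 13 = 7.8 and 0.6 × 190 = 114. All three match.

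**Pooled geometric mean, six fasted doses.** 0.6 × (1 × 3 × 10 × 30 × 100 × 190)^(1/6) = 0.6 × 16.05 = 9.63. Fold = 114 / 9.63 = 11.8.

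**Top-dose exposure divided by pooled mean, other assumptions:**

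| Exposure | 1–300 mg fasted | plus 30 mg fed | plus 600 mg | plus both |
|---|---|---|---|---|
| Linear, 190 mg ceiling | 11.8 | 10.8 | 8.3 | 8.0 |
| Proportional | 17.3 | 16.0 | 20.9 | 20.8 |
| Dose^0.7 | 7.4 | 7.0 | 8.4 | 8.4 |
| Dose^0.7, 190 mg ceiling | 5.6 | 5.3 | 4.4 | 4.3 |
| Dose^0.5, 190 mg ceiling | 3.4 | 3.3 | 2.9 | 2.8 |

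**Effect on the prediction, no treatment offset.** Pooled prediction = top-dose effect / fold. A true 20 ms becomes 20 / 11.8 = 1.7 ms (1.0 to 4.7 ms over the first four rows; up to 7.1 ms in the last). The pooled point prediction reaches 10 ms only when the top-dose effect is 10 × 11.8 = 118 ms (43 to 209 ms over the first four rows). The upper bound reaches it sooner.

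**With a treatment offset a.** Pooled prediction = a + (20 − a) / 11.84. At a = 5 ms this is 5 + 1.27 = 6.3 ms. It reaches 10 ms only at a = (10 − 1.69) / (1 − 0.0845) = 9.1 ms.

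**Simulation of the rule.** 18 subjects on the protocol sequences plus the fed period (18 × 3 + 9 = 63 subject-periods); QTcF at 2 to 24 h; half-life 7 h; between-subject log-SD of Cmax 0.3; ceiling exposure; no offset; model refitted in each resample; unstratified draws; 1,000 trials of 500 resamples. The SDs are assumed. Entries are % of runs.

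| SDs: subject, subject-period, residual (ms) | Pooled rule excludes true 20 ms | 300 mg bound excludes true 20 ms | 300 mg bound excludes true 10 ms | True 0 ms passes at 300 mg and all lower |
|---|---|---|---|---|
| 0, 4, 6 | 100 | 0 | 6.5 | 99.7 |
| 4, 4, 6 | 100 | 0 | 4.7 | 98.2 |
| 4, 6, 9 | 98.3 | 0 | 6.3 | 86.3 |
| 5, 8, 12 | 88.7 | 0 | 4.5 | 64.9 |
| 6, 10, 14 | 77.3 | 0.1 | 5.2 | 49.0 |

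True effects are those at the 300 mg Cmax. Monte Carlo error is about 0.7 points near 5%. At the 4.3-fold exposure setting (draws stratified by dosing interval and treatment), the pooled rule excluded a true 20 ms at 300 mg in 98.7, 74.5 and 60.8% for the second, fourth and fifth SD sets. In the roughly 3-fold setting, smaller simulations gave about 26 to 75%.

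**The case against.** The strongest reply is that the SAP never says the Cmax is pooled. Part A treatment groups are dose levels, ECG results are summarised by group, and Protocol 11.3.2 presents PK parameters by dose. If the prediction was meant per dose, the fold figures do not apply. The separate PK and PK/PD SAPs or the table shells may settle this. That stands as a limit on the size of the problem. It does not rescue the rule: on a per-dose reading the SAP does not say which prediction decides, and defining the mean elsewhere would leave the exclusion sentence unlimited.

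The 4- to 21-fold range is also not a bound. The top end needs the optional 600 mg level with proportional exposure, against the predicted ceiling. A harsher exponent takes the bottom to 2.8. The protocol's own exposure prediction gives 8.0 to 11.8, the fairest single illustration.

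The consequence is limited too. A signal would not be hidden: "Estimates of the regression coefficient and the treatment effect along with their associated 90% confidence intervals (CIs) will be obtained from the model", and in SAP 7.5.1.1 "the change from baseline for each parameter at each post-dose time point will be provided by treatment group". Nothing in either document ties dose escalation to this rule, and QT is not a named objective. All of that stands.

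**Conclusion.** The concern holds. Two defects follow from the text alone: the Cmax has no dose level, and the exclusion has no dose or concentration limit. The size depends on the pooled reading and on assumed exposures. On the protocol's predicted exposure the pooled value lies 8.0 to 11.8 times below the top dose. With linear response, no offset and the assumed SDs, the rule would usually exclude a true 20 ms effect at 300 mg, while the same model read at the 300 mg Cmax would almost never do so. The risk is one over-broad conclusion in the report, contradicted by other planned output. It should be fixed, but it does not threaten the trial.

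**What to change.** Compute the predicted placebo-adjusted change and its 90% interval at the geometric mean Cmax of each Part A dose level, including the highest studied, taking the bootstrap Cmax within that level. Replace the exclusion sentence with one to this effect: an effect of 10 ms or more is excluded up to the highest geometric mean Cmax at which the upper bound there, and at every lower level, does not exceed 10 ms.

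State the resampling scheme; this is secondary. With unstratified draws, a resample contains no 300 mg subject-period with probability (57/63)^63 = 0.0018, about 9 in 5,000, and such resamples are left out of that level's interval. Drawing within dosing interval and treatment avoids the gap, but in the same simulations it wrongly excluded a true 10 ms at 300 mg in 6.2 to 8.9% of runs, against 4.5 to 6.5% unstratified (nominal 5%). Unstratified draws are therefore slightly preferable.

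The cost is two or three SAP sentences and a small program change. The price is a less favourable bound at high exposure. Over both resampling schemes, a drug with no QT effect passes at 300 mg and all lower levels in 98 to 99.7% of runs with the two smallest SD sets, 86 to 90% with the middle set and 49 to 72% with the two largest. When 300 mg fails, a claim at lower exposure often remains: the 100 mg bound taken alone passes in 81 to 100%. The claim up to 100 mg holds somewhat less often with large SDs, because all lower levels must pass too.
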